## 12-Lead Electrocardiogram Report

ECG Performed	$\Box$ YES $\Box$ NO	
DATE	//	
	(dd/mm/yyyy)	
	Abnormal Q-waves	$\Box$ YES $\Box$ NO
	Abnormal ST segment changes	$\Box$ YES $\Box$ NO
	Abnormal T wave inversion	$\Box$ YES $\Box$ NO

## Angiographic Follow up

1. Was angiographic follow-up performed?   YES  NO
2. Was IVUS performed per laboratory guidelines?  VES IVOS NO
3. Was OCT performed per core laboratory guidelines?  VES  NO
4. Were results sent to the core laboratory? $\Box$ YES $\Box$ NO

Site	e ID Subject Number Birth Year			
	12 Month Follow-up Visit			
Dat	e of Subject Visit/Contact:			
	Check if Follow-up (12 months) was not performed and leave the rest of the page blank.			
Gei	neral Assessment			
1.	Did the subject visit the clinic?			
	$\Box$ (1) YES			
	$\Box$ (2) If NO, was the visit conducted via telephone?			
	$\Box(1)$ YES			
	$\Box$ (2) NO			
2.	Were current medications discussed?			
	□ If YES, update the Concomitant Medications Log as appropriate			
	$\Box$ NO			
3.	Did any adverse events occur since last study visit?			
	□ If YES, update the Adverse Event Log			
	□ Did not discuss			
4.	
 
Did the subject have any reinterventions since the last study visit?
 
□ If YES, complete the Intervention/Revascularization Form and record the precluding adverse event on the Adverse Event Log
 
□ NO
 
			

ECG Performed	$\Box$ YES $\Box$ NO $\Box$ NA	
DATE	//	
	(dd/mm/yyyy)	
	Abnormal Q-waves	$\Box$ YES $\Box$ NO
	Abnormal ST segment changes	$\Box$ YES $\Box$ NO
	Abnormal T wave inversion	$\Box$ YES $\Box$ NO

Sit	e ID Subject Number Birth Year			
	24 Month Follow-up Visit			
Dat	te of Subject Visit:             DD       MM       YYYY			
	Check if the visit was not performed			
Gei	neral Assessment			
1.	Did the subject visit the clinic?			
	$\Box$ YES			
	$\Box$ If NO, was the visit conducted via telephone?			
	$\Box$ YES			
	$\Box$ NO			
2.	Were current medications discussed?			
	□ If YES, update the Concomitant Medications Log as appropriate			
	$\Box$ NO			
3.	3. Was the subject asked if any adverse events occurred from the last study visit?			
	□ If YES, update the Adverse Event Log as appropriate			
	$\Box$ NO			
4.	Did the subject have any reinterventions since the last study visit?			
	□ If YES, complete the Intervention/Revascularization Form and record the precluding adverse event on the Adverse Event Log			
	$\Box$ NO			

ECG Performed	$\Box$ YES $\Box$ NO $\Box$ NA	
DATE	//	
	(dd/mm/yyyy)	
	Abnormal Q-waves	$\Box$ YES $\Box$ NO
	Abnormal ST segment changes	$\Box$ YES $\Box$ NO
	Abnormal T wave inversion	$\Box$ YES $\Box$ NO

Site	Birth Year     Subject Number     Birth Year			
	36 Month Follow-up Visit			
Dat	e of Subject Visit:			
	Check if the visit was not performed			
Gei	General Assessment			
1.	Did the subject visit the clinic?			
	$\Box$ YES			
	$\Box$ If NO, was the visit conducted via telephone?			
	$\Box$ YES			
2.	Were current medications discussed?			
	□ If YES, update the Concomitant Medications Log as appropriate			
3.	Was the subject asked if any adverse events occurred from the last study visit?			
	□ If YES, update the Adverse Event Log as appropriate			
4.	Did the subject have any reinterventions since the last study visit?			
	□ If YES, complete the Intervention/Revascularization Form and record the precluding adverse event on the Adverse Event Log			

ECG Performed	$\Box$ YES $\Box$ NO $\Box$ NA	
DATE	//	
	(dd/mm/yyyy)	
	Abnormal Q-waves	$\Box$ YES $\Box$ NO
	Abnormal ST segment changes	$\Box$ YES $\Box$ NO
	Abnormal T wave inversion	$\Box$ YES $\Box$ NO

Site	ID Birth Year Birth Year
	Study Completion/Termination Form
1.	Did the subject complete the entire course of the study? $\Box$ YES $\Box$ NO
	1.1. If yes, date of subject completion:
	DD MM YYYY
	1.2. If no, date of subject termination:
	DD MM YYYY
	1.2.1. Reason for termination (mark only one)
	□ Withdrawal of Consent by the Subject
	□ Lost-to-follow-up
	Date of last contact:
	DD MM YYYY
	Other-Specify:
	□ Death
	Date of Death:
	DD MM YYYY
	Primary Cause of death:
	□ Underlying cause(s) of death:
	Was death related to the study product? $\Box$ YES $\Box$ NO
	Was death related to the study procedure? $\Box$ YES $\Box$ NO
2.	Were any Adverse Events Reported during the course of the study?
	$\Box$ If YES, ensure the Adverse Event Log is up to date.
	$\Box$ NO

Site ID	Subject Number	Birth Year
	CRF Completion Acknowledgem	ent

To be completed by the Investigator: I have assumed responsibility for completeness and accuracy of all data recorded in these Case Report Forms.					
Investigator's Name – Print Clearly	Investigator's Signature				
Date:                DD MM YYYY					

Site ID _____

Subject Number ____ Birth Year ____

# **Comment Log**

Use this form to explain any subject, drug, or product related events that occurred during the study that are not noted elsewhere. Indicate the CRF page number(s) and if applicable study visits to which the comment refers in the appropriate column. Provide description of the event, initials of the study personnel, note the action taken, if any.

 $\Box$  Check if there are not any comments

CPF		Person
	Comment	Recording
rage		Comment

Birth Year __ __ __

CVT ISR Trial FIH Trial Protocol Number: TP1125 Case Report Forms

Site ID ______

Subject Number _____

**Concomitant Medications Log** 

	ta noiti	fi AoshO gainninao Study Termina RaimnoT ybutZ					
	Stop Date (DD/MM/ YYYY)		//  □ Unknown	//	//  □ Unknown	// 	
		Start Date (DD/MM/ YYYY)	//	///	///	///	
	ine)	Vbut2 Medication					
D	ation e per li	Prophylaxis					
	Indic heck one	Adverse 25 Adverse 26					
	⊆ Existing Condition						
		Route (See ** Below)					
		Frequency (See * Below)					
		Unit					
		Dose					
	Drug Name (Generic)	Reminder: Include study medications such as aspirin and clopidogrel. Number all medications in chronological order.					
	# 11	Concomitan Medication					

Page 22 of 28

Site ID _____

Subject Number _____

Birth Year _____

			nt entially.	
//	//  Unknown	//  Unknown	Each concomita numbered seque	
///	//	//	Instructions: ] ation is to be 1	
			medic	
			tion 1al sted	
			H = inhalat = oral = sublingu her = not li	
			ar IN PC IS SL Otj	
			ate: atramuscul atravenous ubcutaneou topical	
			** Rou IM = ii IV = ir SC = s TOP =	
			daily / other day night isted	
			BID = twice QOD = every QHS = every Other = not 1	
			quency: once daily three times a day four times a day a sneeded	
			* Free QD = QD = QD = QID = QID = QID = PRN =	

FRM1123 Rev. 01, DCO#0031. Effective Date: 09-Jun-2021

Page 23 of 28

Site ID ______

Subject Number _____

Birth Year ____

Log
ent
Eve
rse
dve
V

				-		. —			
noizutzan	Check if Trs due to AE					solved ith			
Out com e	See Cod es Belo w						or hour	ered w	
nshi des w	Procedure Procedure					come	Danad	Recov	lelae
Relatio See Co Belo	to Study Device					Out		$5 = \frac{1}{2}$	sedu
erious dverse Jvent ose one)	If yes, See Codes Below					lationshin	- Mot	- 1voi lated	= Unlikely
Se Ac F (cho	No					Re	-	- I Re	с П
Freq uenc Y	See Code s Belo w					odes			ofa
v ne)	Severe					nt Co			ment
everity 00se 01	Moderate					se Eve	daoth	ucauı atenin⊊	imnai
S (ch	piiM					Adver	140 :50	e-thre	tuent
Resolution	DD/MM/ YYYY)	//	//			Serious /	$\mathbf{v} - \mathbf{D}_{\text{odd}}$	A - Resu B = Is life	C = Derm
g of nt ose	qO-i204							a	mittent
Timin Eve (choc one	Intra-Op					requer	- Cuito	– pisode	= Inter
Oucot Data	(DD/MM/YYYY)	//	/_/					on a sign or 1	usual activity or 2
erse Event ribe Event)	ist adverse events lverse event					Severity	Mild – Amonomot	symptom that does	with the subject's u
Adve	Reminder: L in order by ac number.					Study Limb	Tudionto if	the event	ni herunaaa
	Study Limb								
	AE Number								

FRM1123 Rev. 01, DCO#0031. Effective Date: 09-Jun-2021

with the subject's usual activity or

occurred in

Page 24 of 28

2 = Unlikely

C = Permanent impairment of a

1125	
Ę	
ber	
Jum	
otoc	
Pr	
Tria	S
Ξ	orm
rial I	エビ
RI	ebo
L ISI	e R
2 S	Cas

Site ID ______

Subject Number _____

Birth Year _____

3 = Not	recovered/not	resolved	4 = Ongoing (at	6 = Fatal	7 = Unknown			
3 = Possible	4 = Probable	5 = Highly	Probable					
body structure or function	D = In-patient or prolonged	hospitalization	E = Medical/surgical intervention	to prevent life-threatening illness or	injury or permanent impairment	F = Led to fetal distress, fetal death	or congenital abnormality or birth	defect
3 = Continuous								
is transient, resolved without	treatment and with no sequelae.	Moderate = Interferes with the	subject's usual activity and/or	requires symptomatic treatment.	Severe = Symptom(s) causing	severe discomfort and significant	impact of the subject's usual	activity and requires treatment.
the study	Limb.	Y=Yes	N=No	NA=Not	Applicable			

Site ID	Subject N	lumber	Birth Year	
	Intervention/Rev	ascularization	Form	
Revascularization	n #			
1. Revascular	ization date:	 DD	 /IM YYYY	_
1. Was the rev	vascularization involving t	the target lesion? $\Box$	YES 🗆 NO 🗆 No	ot Applicable
2. Was the tar Applicable	get lesion revascularizatio	on ischemia driven?	□ YES	□ NO □ Not
	Intervention	Reason for		
Location	Performed	Intervention	Was the	Was the
1=Right Coronary	(mark only one)	(mark only one)	was the	Intervention
2=Left Anterior	1=Angioplasty	1=Occlusion	Successful? (<	Clinically
Descending	2=Stent (Bare)	2=Stenosis	50% stenosis)	Drivon?
3=Circumflex	3=Stent (Drug Eluting)	3=Thrombosis	5070 stellosis)	Diiven:
	4=Other, specify	4=Other, specify		
$\Box(1)  \Box(2)  \Box(3)$	$\Box(1)  \Box(2)  \Box(3)$	$\Box(1)$ $\Box(2)$	$\Box(1)$ Yes	$\Box(1)$ Yes
	□(4)	□(3)	$\Box$ (2) No	□(2) No
		□(4)		
$\Box(1)  \Box(2)  \Box(3)$	$\Box(1)  \Box(2)  \Box(3)$	$\Box(1)$ $\Box(2)$	$\Box(1)$ Yes	$\Box(1)$ Yes
	□(4)	□(3)	□(2) No	□(2) No
		□(4)		
$\Box(1)  \Box(2)  \Box(3)$	$\Box(1)  \Box(2)  \Box(3)$	$\Box(1)$ $\Box(2)$	$\Box(1)$ Yes	$\Box(1)$ Yes
	□(4)	□(3)	$\Box$ (2) No	□(2) No
		□(4)		
$\Box(1)  \Box(2)  \Box(3)$	$\Box(1)  \Box(2)  \Box(3)$	$\Box(1)$ $\Box(2)$	$\Box(1)$ Yes	$\Box(1)$ Yes
	□(4)	□(3)	□(2) No	□(2) No
		□(4)		

#### Angiographic Assessment

1. Was an angiogram of the study lesion(s) captured during this visit?  $\Box$  YES  $\Box$  NO

1.1. Was the angiogram sent or uploaded to the core lab?  $\Box$  YES  $\Box$  NO

Site ID _____

Serious Adverse Event Notification Form Serious Adverse Type: 1. Reason for SAE: (choose one)  $\Box$  Resulted in Death  $\square$  Is Life-threatening □ Required inpatient hospitalization or prolongation of existing hospitalization □ Resulted in persistent or significant disability/incapacity 2. Date of report: 3. Date of adverse event onset: 4. Type of report:  $\Box$  Initial  $\Box$  Follow-up 5. Diagnosis/Adverse Event (Name must match the AE found on the Adverse Event Log): 6. Symptoms (if applicable): _____ 🗆 NA Relationship to study device (check only one): □ Not Related  $\Box$  Unlikely Related  $\Box$  Possibly Related □ Highly Probable Related □ Probably Related 7. Relationship to study procedure (check only one):  $\Box$  Not Related □ Unlikely Related □ Possibly Related □ Probably Related □ Highly Probable Related 8. Frequency of event:  $\Box$  Single episode  $\Box$  Intermittent  $\Box$  Continuous 9. Outcome of event at this time: 
Recovered/resolved 
Recovered with sequelae  $\Box$  Not recovered/not resolved  $\Box$  Ongoing 🗆 Fatal □ Unknown

Subject Number

Birth Year _____

Site ID __ __ __

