3.4 Other Clinical Endpoints

³ Garcia-Garcia HM, McFadden EP, Farb A, et al. Standardized End Point Definitions for Coronary Intervention Trials: The Academic Research Consortium-2 Consensus Document. Circulation. 2018;137(24):2635-2650. doi:10.1161/CIRCULATIONAHA.117.029289

⁴ Moussa ID, Klein LW, Shah B, et al. Consideration of a new definition of clinically relevant myocardial infarction after coronary revascularization: an expert consensus document from the Society for Cardiovascular Angiography and Interventions (SCAI). J Am Coll Cardiol. 2013;62(17):1563-1570. doi:10.1016/j.jacc.2013.08.720

- Target lesion failure (TLF) at 30 days, 1, 2 and 3 years, post-procedure, defined as a composite rate of cardiovascular death, target vessel myocardial infarction and clinically-driven target lesion revascularization (TLR).
- Target vessel failure (TVF) at 30 days, 180 days and 1, 2 and 3 years post-procedure, defined as a composite rate of cardiovascular death, target vessel myocardial infarction, and target vessel revascularization (TVR).
- Clinically-driven target lesion revascularization (TLR) at 1, 2 and 3 years post-procedure.
- Clinically-driven target vessel revascularization (TVR) at 180 days and 1, 2 and 3 years post-procedure.
- Rate of vascular access site complication, defined as the combined rate of hematoma, AV fistula or a pseudoaneurysm that required intervention, such as surgical repair or transfusion, prolonged hospital stay or required a new hospital admission.
- Lesion success (per device), defined as achievement of a final in-lesion residual diameter stenosis of <30% (by QCA), using any device after wire passage through the lesion. Pre- and post-dilatation of the lesion with a non-study device is considered part of assigned device treatment.
- Technical success (per device), defined as achievement of a final in-lesion residual diameter stenosis of <30% (by QCA), using the CVT Everolimus-coated PTCA Catheter without a device malfunction after wire passage through the lesion. Pre- and post-dilatation are considered part of assigned device treatment.
- Clinical success (per subject) defined as technical success without the occurrence of major adverse events during the procedure.
- Procedural success (per subject) defined as lesion success without the occurrence of major adverse events during the procedure.

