5.5 Serious Adverse Events

An Adverse Event is considered serious if the event led, or might have led, to one of the following outcomes:

- Death of a subject
- Serious deterioration in the health of a subject that resulted in any of the following:
 - o Life-threatening illness or injury
 - Permanent impairment of a body structure or body function
 - o Hospitalization or prolongation of patient hospitalization
 - Medical or surgical intervention to prevent life-threatening illness or injury or permanent impairment to a body structure or body function
 - Chronic disease
- Foetal distress, foetal death or a congenital physical or mental impairment or birth defect

Planned hospitalizations for pre-existing conditions or a procedure required by this protocol without serious deterioration in health is not considered a serious adverse event.

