5.6 Procedures for Reporting Serious Adverse Event

Criteria for Reporting Serious Adverse Event

Serious adverse events are required to be reported for the following situations:

- a. Any serious adverse event that has a causal relationship with the investigational device or the investigation procedure or where such as causal relationship is reasonably possible.
- b. Any device deficiency that might have led to a serious adverse event if appropriate action had not been taken, intervention had not occurred or circumstances had been less fortunate.
- c. Any new findings in relation to any event referred to in points (a) and (b) above.

Reporting by the Sponsor to National Competent Authorities

The Sponsor must report serious adverse events to the National Competent Authorities (NCAs) where the clinical investigation has commenced per the following timelines:

• For all reportable events which indicate an imminent risk of death, serious injury or serious illness and that requires prompt remedial action for other subjects, users

or other persons or a new finding to the event: *Immediately but not later than two* (2) calendar days after awareness by the Sponsor of a new reportable event or of new information in relation with an already reported event.

• For other reportable events or a new finding/update: *Immediately but not later than seven (7) calendar days following the date of awareness by the sponsor of the new reportable event or of new information in relation with an already report event.*

Reporting by the Clinical Trial Investigator to Sponsor

The Clinical Trial Investigator will report to the Sponsor immediately but no later than three (3) calendar days after investigational site study personnel become aware of the event.

Risk Assessment

In conjunction with the Coordinating Clinical Investigator and/or, if need be, the Clinical Event Committee (section 10.2) the Sponsor shall decide whether, as a result of a serious adverse event, the safety of study participants is at risk, or whether continuation of the trial is in jeopardy.

Corrective Measures

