9.8 Reporting Requirements

The investigator should notify the IRB/EC in writing within three months after completion, termination or discontinuation of the study at the site. The same procedure will be applied to Competent Authority where required. A site reporting requirements summary is presented in **Table 3**.

Type of CRF/Report	Time Frame	Process
CRF (baseline, in-hospital summary, follow-up, non-compliance, reconciliation form, subject withdrawal)	Ongoing basis	CRF
Adverse Events	Ongoing Basis	CRF Details to be retrieved at monitoring visit
Serious Adverse Event Notification CRF (including death, device malfunction; failure, near incident, unanticipated adverse device effects)	Within 24 hours	Input within 24 hours of knowledge of event
Annual reports	Annually, as required by Ethic Committee	Material to be prepared by sponsor and copy to be provided to EC by investigator
Final report	Within 6 months of study completion or termination	Material to be prepared by sponsor and copy to be provided to EC by investigator

Table 4. CVT-ISR Study Site Responsibilities for Submitting Data and Reports

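### The SAE Notification Form's list of reasons conflicts with section 5.5 and Table 4, and no legible Procedural Form item asks about the device malfunction on which technical success depends

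*Combined protocol and SAP*

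**What the plan says.** - **Appendix L, Serious Adverse Event Notification Form, item 1.** The site picks a single reason from four: death, life-threatening, "Required inpatient hospitalization or prolongation of existing hospitalization" and "Resulted in persistent or significant disability/incapacity". There is no residual option.
- **Section 5.5.** Seven outcomes make an event serious. They include "Medical or surgical intervention to prevent life-threatening illness or injury or permanent impairment to a body structure or body function", "Chronic disease" and a foetal or congenital category. The section also covers events that could have led to one of these outcomes.
- **Appendix L, Adverse Event Log.** Seriousness is coded A to F. Code E reads "E = Medical/surgical intervention" (to prevent serious harm), and code F covers foetal outcomes.
- **Section 9.8, Table 4.** The form due within 24 hours is described as "Serious Adverse Event Notification CRF (including death, device malfunction; failure, near incident, unanticipated adverse device effects". (Section 5.6 gives the investigator up to three calendar days; that difference is outside this point.)
- **Section 5.6(b).** Reportable events include "Any device deficiency that might have led to a serious adverse event if appropriate action had not been taken".
- **Section 3.4.** Technical success, counted per device, is a final residual stenosis below 30% reached "using the CVT Everolimus-coated PTCA Catheter without a device malfunction after wire passage through the lesion". Clinical success, counted per subject, is technical success with no major adverse event during the procedure. Appendix B defines device malfunction.

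**The concern.** The protocol defines seriousness one way and gives sites a notification form that defines it more narrowly. Take a dissection that is stented at once, with no infarct and no longer stay. If the investigator judges that the stent prevented life-threatening illness or permanent impairment, the event is serious by the intervention criterion alone. The site can code it E on the log, but the notification form has no matching reason. The event may then be forced under a wrong reason or not sent. This matters because the sponsor's two-day and seven-day reporting clocks in section 5.6 start only when the sponsor becomes aware.

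The second gap concerns the device itself. Table 4 names this form as the channel for malfunctions, yet nothing on it asks about one. The Procedural Form does not legibly ask either, so a component of technical success has no structured source. In a first-in-human device study this is basic performance information, and a missed malfunction in an otherwise successful use can only move the rate in the device's favour.

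**Working it through.** The plan gives no figure to reproduce here. The check sets the lists side by side, looks for every other place where the data could be recorded, and then sizes one missed malfunction.

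**1. Seriousness lists**

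| Section 5.5 outcome | AE Log code | SAE form item 1 |
|---|---|---|
| Death | A | yes |
| Life-threatening illness or injury | B | yes |
| Permanent impairment | C | roughly, as disability/incapacity |
| New or prolonged hospital stay | D | yes |
| Preventive medical or surgical intervention | E | none |
| Chronic disease | none | none |
| Foetal or congenital outcome | F | none |

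Seven outcomes less four options leaves three with no option on the form. Two of those three already have a log code, so the two forms disagree with each other as well as with section 5.5.

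**2. Malfunction on the SAE form**

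Item 1 has no option for it and no other item asks about it. Item 5 takes a free-text diagnosis, but its name has to agree with an Adverse Event Log entry. Section 5.1 defines an adverse event through medical occurrence, disease, injury or clinical signs. A malfunction that harms nobody may therefore have no log entry to agree with.

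**3. Malfunction and bail-out elsewhere on the CRF**

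- The Procedural Form records, for each study catheter, maximum pressure, inflation time and duration, and whether inflation lasted a minute. It also records dissection grade, treatment of dissection, the device used and the stent type. Bail-out is therefore captured. No legible item asks about malfunction.
- Item 12 was not legible in the text read for this point. The sub-items after it ask for the device used and the stent type, as those after item 14 do, so it is almost certainly the dissection-treatment question.
- The Comment Log accepts free text on product events, but Table 4 does not list it as a notification route.

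**4. Size of one missed malfunction**

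Inputs: 50 subjects (Protocol Summary) and one or two study catheters each (section 4.3), so N lies between 50 × 1 = 50 and 50 × 2 = 100 devices. If m malfunctions in otherwise successful uses go unrecorded, technical success is overstated by m/N. For m = 1 this is 1/50 = 2.0 points or 1/100 = 1.0 point.

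Section 6.4 specifies exact 95% Clopper-Pearson intervals: lower limit Beta(0.025; x, N − x + 1), upper limit Beta(0.975; x + 1, N − x). As an illustration, suppose every device is recorded as a success:

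| N | Malfunctions missed | True successes | Rate | 95% CI |
|---|---|---|---|---|
| 50 | 0 | 50 | 100% | 92.9 to 100 |
| 50 | 1 | 49 | 98% | 89.4 to 99.9 |
| 50 | 2 | 48 | 96% | 86.3 to 99.5 |
| 100 | 0 | 100 | 100% | 96.4 to 100 |
| 100 | 1 | 99 | 99% | 94.6 to 100 |

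The documents give no malfunction rate, so m cannot be estimated.

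**The case against.** The strongest reply is that the duty to notify comes from sections 5.5 and 5.6 and Table 4, not from a tick list. Table 4 tells sites in words to notify malfunctions, and nothing shows that a site would let a short list override it. There is also room to write: items 5, 11 and 12 of the SAE form, the log's event description and the Comment Log all take free text, and a failed inflation would partly show in the inflation items. This stands to the extent that the data have somewhere to go. It does not remove the conflict, because free text is not a structured source for an endpoint component and item 5 depends on a log entry that may not exist.

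Three stronger readings are tempting, and the documents do not support them.

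- *Bail-outs go unreported.* Section 4.3 requires their justification on the CRF and keeps those subjects in the analyses, and the Procedural Form records the dissection and the stent. What can fail is coding or notification as an SAE. Whether a promptly stented dissection is serious under section 5.5 is also a case judgement.
- *Technical success is overstated.* It can be, but no malfunction rate is given. The effect would come from the missing Procedural Form question, not from item 1.
- *The dissection rate in Appendix J sizes the problem.* That rate is for dissection leading to ischemia or infarction, which is a different group from dissections rescued before harm.

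Two limits also stand. The foetal option has little practical weight, since pregnant and lactating women are excluded. And Appendix L warns that the appended forms may not be current: FRM1123 Rev. 01 is dated 09-Jun-2021, before protocol revision A of 22-Sep-2021.

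**Conclusion.** The form is wrong as written. Item 1 omits three of the seven outcomes in section 5.5 and disagrees with codes E and F of the Adverse Event Log. The form also has no structured entry for the malfunctions, failures and near incidents that Table 4 assigns to it. In addition, no legible Procedural Form item supplies the malfunction component of technical success.

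The consequences are limited. An event that is serious only by the intervention criterion may be miscoded or not notified as an SAE, though a bail-out stays in the data. Technical success can be too high by the 1.0 to 2.0 points per missed malfunction shown above, and clinical success inherits the error. This assumes that the missed malfunction occurred in an otherwise successful use and that between 50 and 100 devices are used. Technical success is descriptive, and neither freedom from TLF at 6 months nor late lumen loss is derived from this item. The conclusion also assumes that the appended CRF is the one in use and that Procedural Form item 12 is not a malfunction question.

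**What to change.** First check whether the current CRF revision already covers this. If it does not:

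1. Replace item 1 of the SAE Notification Form with the full section 5.5 list, matched to Adverse Event Log codes A to F plus chronic disease, and let the site mark more than one.
2. Add a device deficiency or malfunction entry to that form, as Table 4 and section 5.6(b) require, that can be completed without a matching Adverse Event Log entry.
3. Add to the Procedural Form, for each study catheter, a yes/no question on malfunction or deficiency with a description field, and derive technical success from it.

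The cost is one CRF revision and a short notice to sites. The likely downside is a few more notifications and possibly a slightly lower technical success rate. No clinical rule changes.
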